5 GENERAL STATISTICAL CONSIDERATIONS

The primary analysis for the efficacy endpoints will be conducted using data collected through the 12-week treatment period. Data will be cleaned and locked prior to conducting the primary analysis.

The final analysis will be conducted after all subjects have completed their Week 16 or end of study (EOS) visit and after all study data is cleaned and locked.

SAS® version 9.4 or higher will be used for statistical analyses, tabulations, and graphical presentations.

In general, descriptive summaries will be presented by treatment groups (placebo and ESK-001 dose levels) and overall, for values at each visit. The descriptive summary for continuous variables will also be provided for the change from baseline and, if appropriate, for the change from week 12 to week 16. Summaries of continuous variables will include the number of subjects (N), mean, standard deviation (SD), median, Q1, Q3, minimum, and maximum. If there are variables with highly skewed distribution (e.g. log-normal distribution), then the geometric mean and %CV will also be reported in descriptive summaries. Inferential analysis for those variables may be performed after log-transformation as deemed appropriate. Descriptive summaries for categorical variables will include the number and percentage of subjects. Unless otherwise stated, denominators for percentages will be the number of subjects in the analysis population.

Between-group comparisons will focus on the comparative performance of a single ESK-001 dose versus placebo. All statistical tests will be conducted at a 2-sided significance level of 0.05. The corresponding p-values and two-sided 95% confidence intervals will be reported.

In general, baseline is defined as the last non-missing value prior to the first dose date and time. For subjects randomized but not dosed, the last non-missing value prior to the randomization date will be used as baseline. For any additional considerations, refer to each specific data section for details.

In general, efficacy data and other non-safety data will be presented by analysis visits as defined by the analysis visit window. Data collected at unscheduled or early termination (ET) visits will also be mapped to analysis visits as defined in [Appendix B](#). If a value does not fall within an analysis window, it will not be included in the summary analysis or comparative analysis.

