7 EFFICACY ANALYSES

All efficacy analyses will be conducted using the mITT Analysis Population. A sensitivity analysis using the ITT or PP analysis set may be performed as appropriate.

The primary and secondary endpoints are based on the efficacy response at the end of treatment (ie. Week 12).

In general, for responder type analyses, the difference in the proportion of subjects between two treatment arms at Week 12 or other timepoints (eg. Week 4, 8, if applicable) and the corresponding two-sided 95% CI will be calculated using the Fisher's exact test or the Chi-squared test depending on the number of observations (if cell counts are less than 5 then use Fisher's). A test of significance for the difference in proportion between two treatment groups will be performed using the Cochran Mantel-Haenszel (CMH) test adjusting for randomization stratification factors and the corresponding two-sided p-value will be presented.

A non-responder imputation will be applied to responder analyses in which subjects who drop out of the study before Week 12 will be considered as a non-responder at the week 12 visit. No imputation will be applied at any other post-baseline visits. [REDACTED]

For continuous efficacy measurements or scores, the treatment difference in the change from baseline between each active treatment and placebo will be compared using an ANCOVA model, with treatment group, visit and randomization stratification factors as fixed effects and baseline measure as a covariate. An unstructured covariance matrix will be used to model the correlation among repeated measurements (if convergence issues are encountered then compound symmetry covariance matrix will be used instead). Within-group least-squares (LS) means, standard errors (SEs), 2-sided 95% CIs, and p-values will be presented for Week 12 and other timepoints, if applicable.

Some efficacy analyses may also be presented by select subgroups of interest such as baseline PASI, age, BMI, race, gender and prior biologic use categories (refer to [Section 5.2](#)). However, given the small sample size, test for statistical significance will not be conducted for subgroup analyses.

[REDACTED]

[REDACTED]

[REDACTED]

[REDACTED]

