7.1 Primary Efficacy Analyses

7.1.1 *Psoriasis Area and Severity Index*

Disease activity will be assessed by the Psoriasis Area and Severity Index (PASI) which derives a score for the severity of psoriatic lesions by evaluating erythema, induration, and scaling in each of 4 body regions, as detailed in [Appendix C](#).

The primary endpoint is the proportion of subjects achieving $\geq 75\%$ reduction in PASI score (PASI-75) at Week 12.

The proportion of subjects achieving PASI-75 will be summarized for each post-dose timepoint by treatment group. The primary efficacy analysis will compare the proportion of subjects achieving PASI-75 at Week 12 between each active treatment and placebo using the CMH method as described in [Section 7](#). This analysis will be repeated at Weeks 4 and 8.

The absolute value, change and percent change from baseline in PASI score will be summarized using descriptive statistics by timepoint and treatment group. Additionally, the difference in the change from baseline between each active treatment and placebo will be assessed using ANCOVA model as described in [Section 7](#). The analysis will be repeated with percent change from baseline as the dependent variable. Estimates of least-squares (LS) means, SEs, 2-sided 95% CIs and p-values will be presented by treatment group for Weeks 4, 8 and 12.

Absolute PASI scores and the proportion of subjects achieving PASI-75, PASI-90, PASI-100, PASI-50 will also be plotted over time by treatment. The proportion of subjects achieving PASI-50, PASI-75, PASI-90 and PASI-100 at Week 12 by treatment will be presented using a bar chart. The percent reduction in PASI at Week 12 for each individual subject will be presented by waterfall plot. Each treatment group will be presented on a separate plot.

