7.3 Psoriasis Body Surface Area

Measurement of psoriasis body surface area (BSA) involvement is a continuous variable and estimated using the handprint method with the size of a patient's handprint representing $\sim 1\%$ of body surface area involved.

The absolute value and change from baseline in %BSA will be summarized using descriptive statistics by timepoint and treatment group. The absolute value and change from baseline in %BSA will be summarized using descriptive statistics by timepoint and treatment group. Additionally, the difference in the change from baseline between each active treatment and placebo will be assessed using ANCOVA model as described in [Section 7](#). Estimates of least-squares (LS) means, SEs, 2-sided 95% CIs and p-values will be presented by treatment group for Weeks 4, 8 and 12. The absolute value and change from baseline in %BSA over time will be plotted by treatment.

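### The repeated-measures model for continuous scores names neither a baseline-by-visit nor a treatment-by-visit term; specifying both costs little and may sharpen the Week 12 comparisons of change scores, by an amount the documents cannot fix

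*SAP*

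**What the plan says.** SAP Section 7 calls the model for continuous scores an ANCOVA, but it is a repeated-measures model. Its terms are listed as "with treatment group, visit and randomization stratification factors as fixed effects and baseline measure as a covariate", and "An unstructured covariance matrix will be used to model the correlation among repeated measurements", with compound symmetry as the fallback. No interaction is listed.

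The promised output is visit-specific. Section 7 states: "Within-group least-squares (LS) means, standard errors (SEs), 2-sided 95% CIs, and p-values will be presented for Week 12", and adds other timepoints where applicable. Section 7.3 sends %BSA to this model ("the difference in the change from baseline between each active treatment and placebo will be assessed using ANCOVA model") and says that the estimates "will be presented by treatment group for Weeks 4, 8 and 12". Section 7.1.1 does the same for PASI and Section 7.5 for DLQI, NRS and EQ-5D-5L. For PASI and the patient-reported outcomes there is a second run: "The analysis will be repeated with percent change from baseline as the dependent variable".

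On the data used, Section 5 says: "The primary analysis for the efficacy endpoints will be conducted using data collected through the 12-week treatment period". Which visits enter the model is not stated. Skin assessments are scheduled at Weeks 1, 2, 4, 8 and 12. Patient-reported outcomes start at Week 2 (SAP Appendix B, Tables 2 and 3). Some text in Section 7 is redacted, but the sentence that lists the model terms is complete.

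**The concern.** Change from baseline starts near zero for everyone. Entry requires BSA of at least 10% and PASI of at least 12, so patients differ mainly in how far above those floors they start. If improvement is roughly in proportion to starting disease, the regression of change on baseline is shallow at Week 1 and steeper at Week 12. A single pooled slope is then wrong at Week 12, and baseline variation that could have been removed stays in the Week 12 residual.

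The second gap is linked to the first. Without treatment-by-visit, the model has one treatment difference shared by all visits, so the Week 4, 8 and 12 comparisons with placebo would be the same number.

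At stake is the precision of Week 12 change in %BSA and DLQI (secondary endpoints), change in NRS and EQ-5D (exploratory), and the supportive PASI change analysis, with 35 patients per arm. In the simulations the two models gave closely similar average estimates, so this is a matter of efficiency rather than bias.

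**Working it through.** **1. The plan's own figure.** The only precision figure is the PASI-75 power (SAP Section 4): 35 per arm, 60% against 10%, two-sided 0.05. With pooled rate 0.35, z = (0.5·√35 − 1.96·√(2·0.35·0.65)) / √(0.6·0.4 + 0.1·0.9) = (2.958 − 1.322)/0.574 = 2.85, so power is 99.8%. An exact Fisher calculation gives 99.5%. The stated figure of at least 99% holds. It says nothing about the continuous scores, for which no SD, slope or correlation is given.

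**2. Algebra (large sample, complete data).** Let Σ be the residual covariance across visits, β_t the true slope of change on baseline at visit t, s_b the baseline SD, and 1 the vector of ones. The common slope that the model estimates is g = 1′Σ⁻¹β / 1′Σ⁻¹1. Put d = β − g1, so that 1′Σ⁻¹d = 0.

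- *Treatment-by-visit present:* SE(by-visit slope)/SE(common slope) at Week 12 = √[Σ₁₂ / (Σ₁₂ + s_b²(β₁₂ − g)²)], where Σ₁₂ is the Week 12 residual variance. The gain depends on how far the Week 12 slope lies from the pooled one.
- *Treatment as a main effect only:* the treatment variance is proportional to 1/(1′Σ_f⁻¹1), with Σ_f = Σ + s_b²dd′. Because 1′Σ⁻¹d = 0, 1′Σ_f⁻¹1 = 1′Σ⁻¹1. The ratio is exactly 1, so there is no gain.

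**3. Simulation.** Trials of 6 × 35 were simulated with improvement proportional to baseline and unstructured covariance. Three sets used different assumed inputs. Set A assumed baseline SDs of about 6 (PASI), 14 (%BSA) and 6.5 (DLQI), and Week 12 improvement from 25% on placebo to 80% at the top dose. The resulting slopes ran from about −0.07 at Week 1 to −0.55 at Week 12. The table shows the percentage reduction in the Week 12 model SE from adding baseline-by-visit, with treatment-by-visit in both models. The reduction in empirical SD, where reported, is in brackets.

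| Score | Visits modelled | Set A | Set B | Set C |
|---|---|---|---|---|
| PASI change | 1, 2, 4, 8, 12 | 16–18 (13) | 14 (13) | 15 (12) |
| PASI change | 4, 8, 12 | about 4 (4) | 7 (2) | 5 |
| %BSA change | 1, 2, 4, 8, 12 | 30–32 (28) | 28 (17) | 24 (8) |
| %BSA change | 4, 8, 12 | 9–10 (12) | 17 (21) | 9 |
| DLQI change | 2, 4, 8, 12 | about 9 | 23 (21) | – |
| DLQI change | 4, 8, 12 | about 2 | 16 (11) | – |

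Set A was also run with 15% dropout. The model SE gains were similar, but the empirical SD sometimes fell much less: for %BSA, 2.055 to 1.906 with all visits (7%) and 2.186 to 2.185 with Weeks 4, 8 and 12.

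Further results from set A:
- *Main effect only:* gain 0.0–0.6%, as the algebra predicts. The SE is smaller there (0.552 for %BSA, all visits, against 1.821 with both interactions), but it belongs to one effect pooled over visits, not to the Week 12 difference.
- *Percent change from baseline* (PASI and %BSA, treatment-by-visit in both models): the model SE changed by −0.3% to −0.1%, so no gain.
- *Grid in the formula* (Week 12 residual SD 0.7–1.2 times baseline SD, residual correlation 0.5–0.8): 0–45%, and exactly 0 when the slope is constant.

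**4. Why the visit list matters.** Take PASI in set A (s_b about 6, Week 12 slope −0.55) and use SE ≈ residual SD × √(2/35), where √(2/35) = 0.239.
- *Weeks 1–12:* SE 1.490 falls to 1.224. Residual SD = 1.224/0.239 = 5.12. Slope gap = (5.12/6)·√[(1.490/1.224)² − 1] = 0.59, so the pooled slope is about +0.04, near the Week 1 value.
- *Weeks 4, 8, 12:* SE 1.280 falls to 1.231. Residual SD = 5.15. Gap = (5.15/6)·√[(1.280/1.231)² − 1] = 0.24, so the pooled slope is about −0.31, against a Week 4 slope of −0.30.

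Here the pooled slope sits close to that of the earliest modelled visit. Including early visits is what makes the common slope costly at Week 12.

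**The case against.** The strongest reply is that Section 7 is terse. It promises visit-specific estimates, so the author may have intended both interactions, and redacted text nearby may bear on this. If the sentence is read literally instead, adding baseline-by-visit changes nothing. Both halves are fair. The answer is to specify the two terms together, because the listed terms do not deliver the promised Week 12 contrast.

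A reader might infer that the missing term costs a fixed 10–20% of precision on every continuous endpoint. The documents do not support that. They give none of the inputs. Proportional improvement was built into the simulations, and the result moves with the visits modelled. Patient-reported outcomes are not collected at Week 1 and have no entry floor, so the mechanism is less secure for them. NRS and EQ-5D were not simulated.

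A reader might also infer that dose selection or the primary result is weakened. The primary analysis is a CMH test of PASI-75. Active doses are compared with each other on PASI-75 (SAP Section 7.2.1), whereas the continuous model compares each dose with placebo. Neither inference stands.

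**Conclusion.** The point holds as an inexpensive gain in efficiency and a gap in specification. As written, one baseline slope is imposed on all visits, and no term allows the treatment difference to vary by visit.

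With treatment-by-visit in place, letting baseline act by visit lowers the Week 12 SE for change scores by roughly 2–17% if only Weeks 4, 8 and 12 are modelled, and by roughly 9–30% if earlier visits enter. Empirical SDs fell less in several runs and hardly at all in one. The gain is zero if the slope is constant or if treatment is a main effect only, and nil in the percent-change runs. All sizes rest on assumed SDs, slopes and correlations. The direction rests on the slope of change on baseline growing over time, which is plausible but not documented.

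**What to change.** In SAP Section 7, list the fixed effects as treatment, visit, treatment-by-visit, stratification factors, baseline and baseline-by-visit. Name the visits in the model for each score, and state that the Week 12 difference from placebo is the contrast of interest.

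Baseline-by-visit adds visits minus one parameters: two with Weeks 4, 8 and 12, three with Weeks 2–12, four with Weeks 1–12. Treatment-by-visit adds (6 − 1) × (visits − 1), that is 10 to 20, but the visit-specific comparisons need it in any case. With about 210 patients this is affordable, and no new data are required. If the slope turns out constant, almost nothing is lost. The change should be made before unblinding, when the SAP is due to be final, so that the term cannot look chosen from the results.

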4 DETERMINATION OF SAMPLE SIZE

The sample size is determined based on the primary efficacy endpoint. Calculations are based on a 1:1:1:1:1:1 randomization ratio (ESK-001 doses 1-5 vs. placebo) and will provide at least 99% power to detect 50% increase in the PASI-75 response rate in an active arm (i.e., 60% response rate) compared to the placebo assuming the response rate is 10% in the placebo arm. With a two-sided, two-sample test at a significance level of 0.05, a sample size of 35 patients per arm for a total of 210 patients is planned.

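### If the unstructured model fails to converge, the SAP's only visible fallback is compound symmetry, which gives a correct Week 12 standard error only if Week 12 variance equals the average over visits (minor; continuous endpoints only)

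*SAP*

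**What the plan says.** SAP Section 7 analyses change from baseline in the continuous measures with a model "with treatment group, visit and randomization stratification factors as fixed effects and baseline measure as a covariate". On the covariance it states: "An unstructured covariance matrix will be used to model the correlation among repeated measurements". The fallback follows in parentheses: "if convergence issues are encountered then compound symmetry covariance matrix will be used instead".

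The model is used for PASI change (Section 7.1), %BSA (Section 7.3) and DLQI, pruritus NRS and EQ-5D (Section 7.5). For PASI the required output is: "Estimates of least-squares (LS) means, SEs, 2-sided 95% CIs and p-values will be presented by treatment group for Weeks 4, 8 and 12". Sections 7.3 and 7.5 ask for the same three weeks. %BSA and DLQI change at Week 12 are secondary endpoints (SAP Section 2).

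On significance, Section 5 says: "All statistical tests will be conducted at a 2-sided significance level of 0.05". Section 5.4 makes no multiplicity adjustment.

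The visible text names no heterogeneous-variance structure, no sandwich standard error and no degrees-of-freedom method. It does not say which visits enter the model. Parts of Section 7 after the model paragraph are redacted, so these absences concern the visible text only.

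**The concern.** An unstructured matrix gives each visit its own variance. Compound symmetry gives all visits a single variance and a single correlation. Under the fallback, the standard error at Week 12, the visit at which the endpoints are defined, is therefore set partly by earlier visits.

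There is a reason to think those variances differ. The model adjusts for baseline. If the raw SD were constant, the residual variance at a visit would be proportional to 1 − ρ², where ρ is that visit's correlation with baseline. That correlation usually weakens with time, and responders and non-responders separate during treatment, so residual variance may well be larger at Week 12 than at Weeks 1 and 2. If it is, the Week 12 intervals are too narrow and the p-values too small. With no multiplicity control, those p-values would be read at face value.

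**Working it through.** **The plan's own figure.** Neither document gives a type I error, SD or correlation for this model. The only related figure is the power for the primary endpoint. The plan is "a sample size of 35 patients per arm for a total of 210 patients is planned", with a 60% rate in an active arm and "assuming the response rate is 10% in the placebo arm". Pooled normal approximation, mean rate 0.35:

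- SE under the null = √(2 × 0.35 × 0.65 / 35) = 0.1140
- SE under the alternative = √((0.09 + 0.24) / 35) = 0.0971
- z = (0.50 − 1.96 × 0.1140) / 0.0971 = 2.85, so power = 99.8% (99.5% with Fisher's exact test)

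The stated power of at least 99% is reproduced. It concerns a CMH test that does not use the repeated-measures model.

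**Formula for the fallback.** With a treatment-by-visit term and complete data:

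- ratio = compound-symmetry SE at Week 12 / true SE = √(mean of the visit variances) / (Week 12 SD)
- type I error = 2 × [1 − Φ(1.96 × ratio)]

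Example with assumed SDs 5, 5.5, 6, 6.5, 7 at Weeks 1, 2, 4, 8, 12 (the skin-assessment visits to Week 12 in SAP Appendix B). The mean variance is (25 + 30.25 + 36 + 42.25 + 49) / 5 = 36.5. The ratio is √36.5 / 7 = 0.86 and the type I error is 9.1%.

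For the four PRO visits (Weeks 2, 4, 8, 12), assumed SDs 5, 5.5, 6, 6.5 give √33.375 / 6.5 = 0.89 and 8.2%. For assumed SDs 3, 4, 5.5, 7, 7.5 the ratio is √32.1 / 7.5 = 0.76 and the error 13.9%. With equal steps from 3 to 7.5 the error is 15.2%, so the path matters as well as the end points.

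**Range of assumed patterns.** SDs are relative, over Weeks 1/2/4/8/12 unless stated. The simulation used 6 arms of 35, AR(1) correlation 0.8, a REML compound-symmetry fit with treatment-by-visit, and 2,000 runs per cell. Its Monte Carlo SE is about 0.5 points at a 5% rate.

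| Assumed SD pattern | Ratio | Formula | Simulated, 0% / 15% dropout |
|---|---|---|---|
| Flat | 1.00 | 5.0% | 3.7% / 5.1% |
| 0.8, 0.85, 0.9, 0.95, 1 | 0.90 | 7.7% | 6.5% / 8.3% |
| 0.5, 0.6, 0.75, 0.9, 1 | 0.77 | 13.0% | 12.0% / 13.9% |
| 0.3, 0.4, 0.6, 0.85, 1 | 0.68 | 18.1% | 18.0% / 20.1% |
| Weeks 4/8/12 only: 0.9, 0.95, 1 | 0.95 | 6.2% | 6.1% / 7.1% |
| Weeks 4/8/12 only: 0.75, 0.9, 1 | 0.89 | 8.1% | 9.4% / 9.3% |
| Hump: 0.8, 1, 1.1, 1.05, 0.9 | 1.08 | 3.4% | 2.9% / 3.9% |
| Falling: 1.3, 1.25, 1.2, 1.1, 1 | 1.17 | 2.1% | 2.7% / 3.2% |

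**Model with only the listed terms.** Without a treatment-by-visit term, simulated type I error was 4.4–6.2% over all eight patterns and both dropout rates. In complete balanced data the compound-symmetry SE of the treatment main effect equals the SE from the patients' own means over visits, so unequal visit variances do not inflate it. That effect is an average over visits, however, and not a Week 12 effect.

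**Alternatives.** In the same simulations, compound symmetry with a sandwich SE and the treatment-by-visit term gave 4.6–7.3%. A Week 12-only ANCOVA gave 3.6–6.0%.

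**How likely is the fallback?** With five visits an unstructured matrix has 5 × 6 / 2 = 15 parameters. With four it has 10. About 210 patients supply up to 210 × 5 = 1,050 observations, so failure to converge is unlikely.

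**The case against.** The strongest case against the point has four parts.

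1. **The listed model does not inflate.** Section 7 lists no treatment-by-visit term, and with the listed terms the error stays near 5%. This is correct as a calculation. But that model gives one identical dose-versus-placebo difference at Weeks 4, 8 and 12, which does not fit the estimates required by week or endpoints defined at Week 12. A by-visit treatment effect is the reasonable reading of what is intended, and it is the model exposed to the problem. The missing term needs correcting in any case.

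2. **The direction is not established.** Compound symmetry does not by itself make the Week 12 SE too small. Variance could peak early or fall as skin clears, and the test is then conservative. Neither document supplies SDs by visit. This stands: rising variance is plausible but assumed.

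3. **The reach is small.** The fallback needs an unlikely convergence failure. PASI-75, including the between-dose comparison, and sPGA 0/1 are tested by CMH. Of the secondary efficacy endpoints only %BSA and DLQI use this model, and their p-values are nominal. This stands and sets the severity.

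4. **Redaction.** A robust SE or further fallback could sit in redacted text. This cannot be excluded.

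**Conclusion.** The point holds as a minor one. If the unstructured fit fails and a by-visit treatment effect is estimated, the Week 12 SE is correct only when Week 12 residual variance equals the average over visits. For moderate assumed rises the nominal 5% test runs at about 8–14%. With only Weeks 4, 8 and 12 in the model the formula gives about 6–8%, and falling or humped patterns give about 2–3%. All visit SDs, the correlation of 0.8 and the 15% dropout are assumptions.

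A reader might infer that the fallback always produces false positives, at rates up to 22%. The documents do not support that. With equal variances the error is 5%, and the direction depends on SDs that neither document reports. A rate of 22% needs a Week 12 SD about 1.60 times the root-mean-square SD over visits, against 1.12 times for 8%. Nor does the point bear on the primary PASI-75 result.

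Severity: optional to minor. It is worth raising because a fallback fixed in advance should be valid when it is used, and the repair is cheap.

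**What to change.** In SAP Section 7, replace the single fallback with an ordered list that keeps a separate variance for each visit: heterogeneous Toeplitz, then heterogeneous AR(1), then heterogeneous compound symmetry, each with empirical (sandwich) standard errors. If all fail, use an ANCOVA on Week 12 alone. In the same edit, add the treatment-by-visit term that the Week 4, 8 and 12 estimates require, and state which visits enter the model and the degrees-of-freedom method.

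The simulations tested the sandwich SE on compound symmetry and the Week 12-only ANCOVA; the heterogeneous structures were not simulated. The sandwich rate reached 7.3% in one setting (falling variance, 15% dropout) with a normal critical value, which is a reason to state the reference distribution.

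The cost is a few lines of SAP text and code, and possibly slightly wider Week 12 intervals. The last step, Week 12 alone, leaves out patients with no Week 12 value, because Section 5.3 does not in general impute missing data. It therefore belongs at the end of the list.
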